5 TYPE OF PLANNED ANALYSIS

5.1 Interim Analysis

There is no interim analysis planned for this study.

5.2 Primary Analysis

After the last enrolled and randomized subject has completed all Day 45 assessments or been lost to follow-up, all outstanding data queries related to the primary and key secondary endpoints have been resolved or adjudicated as unresolvable, and the data have been cleaned and finalized, the study blind will be broken, and the primary analysis will be performed. The primary analysis will be performed using ITT population as detailed in **Table 1**.

Table 1: Summary of Primary and Key Secondary Endpoints at Day 45

Endpoint	Display	ITT	PTE	Sensitivity	Subgroup
Primary					
Patency based on cross-sectional area of FSO on CT by an independent, blinded reviewer	T,L	Y	-	Y	Y
Key Secondary Adjusted for Multiplicity					
Cross-sectional area of FSO on CT change from baseline	T,L	Y	-	-	-
FSOT volume on CT	T,L	Y	-	-	-
FSO minimum diameter on CT	T,L	Y	-	-	-
Zinreich's score for frontal sinus	T,L	Y	-	-	-
Need for post-op interventions in the frontal recess/FSO	T,L	Y	-	-	-

Abbreviations: CT, computed tomography; FSOT, frontal sinus outflow tract; ITT, intent to treat; L, listing; PTE, per treatment evaluable; T, table; Y, yes.

5.3 Secondary and Exploratory Analyses

The secondary and exploratory analyses through Day 180 (end of study) will be performed after completing primary analysis and after the database is locked, using analysis populations and endpoints detailed in

Table 2.

Table 2: Summary of Secondary and Exploratory Analyses

Endpoint	Display	ITT	PTE
Secondary			
Cross-sectional area of FSO on CT (Day 180)*	T,L	Y	-
FSOT volume on CT (Day 180)*	T,L	Y	-
FSO minimum diameter on CT (Day 180)*	T,L	Y	-
Lund-Mackay score for the frontal sinus (Day 45, 180)*	T,L	Y	-
Zinreich's score for the frontal sinus (Day 180)*	T,L	Y	-
Lund-Mackay score for the frontal sinus (Day 45, 180)**	T,L	Y	-
Need for post-operative interventions in the frontal recess/FSO (Day 21, 90, 180)**	T,L	Y	-
Adhesion/scarring grade in the frontal recess/FSO and ethmoid sinus (Day 21, 45, 90, 180)**	T,L	Y	-
Polypoid edema in the frontal recess/FSO (Day 21, 45, 90, 180)**	T,L	Y	-

CONFIDENTIAL

10 of 33

May not be reproduced outside of Intersect ENT without written permission from Document Control

Endpoint	Display	ITT	PTE
Inflammation score in the frontal recess/FSO (Day 21, 45, 90, 180)**	T,L	Y	-
Polyp grade in the ethmoid sinus (Day 21, 45, 90, 180)**	T,L	Y	-
CRS side-specific score (Day 21, 45, 90, 180)	T,L	-	Y
SNOT-22 score (Day 180)	T,L	-	Y
RSI score (Day 180)	T,L	-	Y
Implant delivery success rate	T,L	Y	-
Exploratory			
Patient satisfaction (Day 90, 180)	T,L	-	Y
Health-economic measures (Day 180)	T,L	-	Y

Abbreviations: CRS, chronic rhinosinusitis; CT, computed tomography; FSO, frontal sinus ostium; FSOT, frontal sinus outflow tract; ITT, intent to treat; L, listing; PTE, per treatment evaluable; RSI, Rhinosinusitis Symptom Inventory; SNOT, Sino-Nasal Outcome Test; T, table; Y, yes.

* By an independent, blinded reviewer.

** By clinical investigators.

6 STATISTICAL METHODS

6.1 General Considerations for Data Analysis

All analyses described in this plan are considered a priori analyses in that they have been defined prior to locking the database and reviewing unblinded results. All other analyses, if any, designed subsequent to locking the database will be considered post-hoc analyses and will be considered exploratory. Any post hoc analyses will be clearly identified in the clinical study report.

Continuous data such as cross-sectional area of FSO, FSO minimum diameter, FSOT volume, inflammation score, CRS side-specific symptom score, SNOT-22 score, and RSI score will be summarized in terms of the mean, standard deviation (SD), median, minimum, maximum, and number of observations, unless otherwise stated.

Categorical data such as Lund-Mackay score, Zinreich's modified Lund-Mackay score, adhesion/scarring grade, polypoid edema grade, and polyp grade will be analyzed quantitatively and summarized in terms of the mean, standard deviation (SD), median, minimum, maximum, and number of observations, unless otherwise stated.

Categorical data such as need for post-operative intervention in the frontal recess/FSO, patient satisfaction, implant delivery success rate, and economic measures will be summarized in terms of the number of subjects providing data at the relevant time point, frequency counts and percentages. If not stated otherwise, percentages will be presented with one decimal place. Percentages will not be presented for zero counts. Percentages will be calculated using n as the denominator. 100% will be presented without decimal places. Frequency distributions showing

findings by treatment side will be presented with counts, percentages and, where appropriate, exact 95% CI using the Clopper and Pearson method.

P-values greater than or equal to 0.001, in general, will be presented to 3 decimal places. P-values less than 0.001 will be presented as “< 0.001”.

95% Confidence intervals (CI) will be presented to 1 more decimal place than the raw data. Unless stated otherwise, a two-sided 95% confidence level will be calculated when confidence interval is presented.

Data from the protocol-specified visits (i.e., as reported in the case report form, CRF) will be used in the summary tables and data listings.

All statistical tests will be two-sided and interpreted at a 5% significance level. A p-value < 0.05 will be considered statistically significant. Unless stated otherwise, a two-sided 95% CI will be calculated and presented.

All available data at each time point will be presented. No imputations for missing data are planned, unless indicated otherwise.

6.2 Baseline

The baseline is defined as the last observation recorded prior to the initiation of the study treatment (i.e., PROPEL Contour placement on the treatment site following successful BSD procedure) and referred to as Day 0.

6.2.1 Study Day Calculation

Study day is calculated relative to the date of Day 0 (baseline) and will appear in the listings where applicable. If the date of event is on or after Day 0, study day will be calculated as:

Study day = date of event – date of Day 0

6.3 Randomization

Following frontal BSD, eligible subjects will have their sinus sides randomly assigned to receive the PROPEL Contour (treatment) on one side, and no implant (control) on the contralateral side. The ratio of left to right sinus assignments will be 1:1. The randomization scheme will be generated by an independent statistician, and the randomization envelopes will be assembled by an in-house clinical research associate. The randomization scheme will be stratified by each clinical center, and will use permuted blocks of various sizes.

6.4 Role of the Independent Reviewer

The CT scans at Screening, Day 45 and 180 from all subjects will be evaluated by an independent, blinded reviewer, a role assumed by the centralized imaging core lab, for determination of the

primary and CT-related secondary efficacy endpoints. The reviewer will be independent from the study (i.e., not enrolling study subjects for the study) and blinded to implant treatment assignment (i.e., will not know which side received PROPEL Contour). CT scans will be labeled with subject ID and be provided to the independent reviewer.

The primary efficacy endpoint requires precise measurements of the FSO using reconstructed cone beam images in the axial, coronal and sagittal planes. The image reconstructions and measurements of CT-related endpoints will be performed by board-certified independent radiologists at the centralized imaging core lab in accordance with the standardized protocol (see CP-00038). The reviewers will be blinded to treatment assignment and have no access to any symptomatic or endoscopic outcomes.

6.5 Relative Difference Calculation

Relative side-to-side difference at any timepoint will be calculated as:

$$[\text{Value}_{(\text{treatment side})} - \text{Value}_{(\text{control side})}] / \text{Value}_{(\text{control side})} \times 100$$

A negative relative difference reflects a decrease in a given parameter on the treatment side compared to control, while a positive relative difference reflects an increase in the parameter on the treatment side compared to control.

6.6 Missing Dates

In analysis of AEs and medication, a complete date will be established in order to identify AEs or medication as occurring during treatment or not. For handling partially reported onset/start and outcome/end dates for AEs or medication the following algorithms are applied:

- AEs:
 - Missing onset day, but month and year present:
 - If baseline visit occurred in the same month and year as the occurrence of the AE, then the onset day of the event is assigned to the date of baseline visit.
 - Otherwise, the onset day is set to the first day of the month (e.g., XX-Sep-2021 is considered as 01-Sep-2021).
 - Missing onset day and month, but year present:
 - If baseline visit occurred in the same year as the occurrence of the AE, then the onset date of the event is assigned to the date of baseline visit.
 - Otherwise, the onset day and month is set to 01 January (e.g., XX-XXX-2021 is considered as 01-Jan-2021).

- Missing outcome day, but month and year present:
 - The day is set to the last day of the month (e.g., XX-Sep-2021 is considered as 30-Sep-2021).
- Missing outcome day and month, but year present:
 - The outcome day and month is set to 31 December (e.g., XX-XXX-2021 is considered as 31-Dec-2021).
- Medications:
 - Missing start day, but month and year present:
 - If baseline visit occurred in the same month and year as the occurrence of the medication, then the start day of the medication is assigned to the date of baseline visit.
 - Otherwise, the start day is set to the first day of the month (e.g., XX-Sep-2021 is considered as 01-Sep-2021).
 - Missing start day and month, but year present:
 - If baseline visit occurred in the same month in the same year as the occurrence of the medication, then the start date of the medication is assigned to the date of baseline visit.
 - Otherwise, the start day and month is set to 01 January (e.g., XX-XXX-2021 is considered as 01-Jan-2021).
 - Missing stop day, but month and year present:
 - The day is set to the last day of the month (e.g., XX-Sep-2021 is considered as 30-Sep-2021).
 - Missing stop day and month, but year present:
 - The stop day and month is set to 31 December (e.g., XX-XXX-2021 is considered as 31-Dec-2021).

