6.7 Missing Data for Efficacy and Safety Endpoints

Missing data for each efficacy endpoint will be handled as described in Sections 9.1 and 9.3.4.

For continuous endpoints, change from baseline will be set to missing at visits with missing postbaseline values or where data were imputed to missing. Continuous efficacy endpoints will be set to missing for subjects who received any of the following not allowed medication post-baseline procedure:

- Corticosteroids (e.g., oral, parenteral or injection, budesonide or other sinus steroid irrigations/rinses or drops, breath powered Xhance, nebulized steroids administered nasally or other drug eluting stents) through Day 45; or
- Biologics for CRS treatment (e.g., Dupixent).

For binary endpoints, subjects with missing efficacy data, early withdrawals, and/or subjects who received not allowed corticosteroids or biologics for chronic sinusitis condition attributable to the FSO/frontal recess will be imputed as a treatment failure. If a subject initiates high-dose steroid for other reasons not involving FSO/frontal recess, this does not represent treatment failure.

Additional rules for handling of missing data and rescue treatments are detailed below:

- *Missing efficacy data.* Visits with missing data (due to a missed visit or missing component of a composite endpoint) will be set to treatment failure.
- *Early withdrawals.* Only visits following the early withdrawal visit will be set to treatment failure.
- *Rescue treatments.* Subjects who rescue with corticosteroids (before Day 45) or biologics will be set to treatment failure at all subsequent visits and continuous endpoints set to missing.
- *Missing baseline value.* For efficacy endpoints, a missing value at baseline will not be imputed, and the endpoint will be set to missing for all visits.

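### SAP 6.6 can place the start of a drug or adverse event at the procedure although its recorded end is earlier, and so class a prior record as during treatment

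*SAP*

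**What the plan says.** SAP 6.6 states the purpose of its date rules: "In analysis of AEs and medication, a complete date will be established in order to identify AEs or medication as occurring during treatment or not". The rules that matter here are these.

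- **Drug, start day missing.** If month and year match the baseline visit, "then the start day of the medication is assigned to the date of baseline visit". Otherwise the first of the month is used.
- **AE, onset day missing.** Under the same condition, "then the onset day of the event is assigned to the date of baseline visit".
- **AE, onset day and month missing.** The condition is "If baseline visit occurred in the same year as the occurrence of the AE", and the onset then becomes the baseline date. Otherwise it is 1 January.
- **Partial stop or outcome dates.** These go to the end of the month, or to 31 December. A complete stop or outcome date is left as recorded.

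None of the start or onset rules refers to the stop or outcome date.

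SAP 6.7 then says: "Continuous efficacy endpoints will be set to missing for subjects who received any of the following not allowed medication post-baseline procedure". Its list is corticosteroids through Day 45, and biologics for CRS. For binary endpoints, such use counts as treatment failure when it is for a sinus condition attributable to the FSO or frontal recess. Section 6.7 does not cite 6.6. It does not say whether the start or the stop date, recorded or imputed, decides that a drug was received after the procedure. SAP 6.1 plans no imputation unless stated otherwise, so an area set to missing leaves the primary t-test.

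**The concern.** Moving an unknown start to the procedure date is a usual cautious choice when the record could belong to either side of Day 0. It is not cautious when the recorded end is already before Day 0. The record is then known to be prior, and the rule overrides that knowledge.

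Three things are at stake. SAP 9.9 tabulates concomitant medications, and a drug that ended before the procedure can enter that table. SAP 9.7 lists start date, stop date and onset study day for each AE, so a screening event that had resolved can appear with onset on Day 0 and an end before its onset. And if a programmer feeds the imputed start into 6.7, a permitted pre-procedure steroid can look like a prohibited post-procedure one and cost the subject's primary value.

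**Working it through.** **1. The plan's own figure.** SAP 4.4 gives a mean side-to-side difference of 9 mm², SD 18 mm², two-sided alpha 0.05 and 56 subjects for at least 95% power. The standardized difference is 9/18 = 0.5. For a one-sample t-test on the paired differences, the noncentrality is 0.5 × √n with n − 1 degrees of freedom. At n = 56 it is 0.5 × 7.48 = 3.74 and power is 95.69%. The smallest n that reaches 95% is 54 (95.02%). The stated figure is reproduced.

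**2. The date rule applied literally.** The dates are assumed for illustration, with baseline on 20-Sep-2021.

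| Record | 6.6 as written | End date respected |
|---|---|---|
| Drug, XX-Sep-2021 to 04-Sep-2021 | start 20-Sep, 16 days after its stop | start 01-Sep, prior |
| AE, XX-Sep-2021 to 10-Sep-2021 | onset 20-Sep, 10 days after its end | onset 01-Sep, prior |
| AE, XX-XXX-2021 to 10-Sep-2021 | onset 20-Sep, 10 days after its end | onset 01-Jan, prior |
| Drug, XX-Sep-2021 to XX-Sep-2021 | 20-Sep to 30-Sep | undetermined; query |

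The first three rows are impossible orderings. The fourth looks valid, so a check for start after stop would not find it. Drugs with day and month both missing do not show the fault. Their condition, "If baseline visit occurred in the same month in the same year as the occurrence of the medication", cannot be evaluated without the month, and the fallback is 1 January. That is a separate slip in wording.

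**3. Which steroids can reach 6.7 by this route in eligible subjects.** The course must have ended before the procedure, outside the washout window, and in the same calendar month.

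- *Oral, rinse or drop, nebulized* (protocol exclusion s, 14 days): the stop is at least 15 days earlier. With a stop on day 1 at the earliest, the procedure falls on day 16 or later. That is 365 − 12 × 15 = 185 of 365 dates (51%).
- *Parenteral or injected* (exclusion r, 30 days): 0 of 365.
- *Biologics* (protocol section 14, 45 days): 0 of 365.

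The 51% is an outer bound, because on day 16 only a one-day course on day 1 fits. If a 5-day course is assumed, the procedure must be on day 20 or later: 365 − 12 × 19 = 137 dates (38%). For a 10-day course it is day 25 or later: 365 − 12 × 24 = 77 dates (21%). The start day must also be missing. Breath-powered fluticasone is on the 6.7 list but is not named in exclusions r or s, so this count does not cover it.

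**4. AEs.** No washout applies, so an earlier end in the same month is possible for any baseline after the first: 365 − 12 = 353 of 365 dates. The real opportunity is smaller. AEs are recorded only from consent, and the procedure follows within about 30 days, sometimes on the same day.

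**5. Power if primary pairs are lost.** The 64 assumes 80 × (1 − 0.20) evaluable.

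| Evaluable | None lost | 1 lost | 2 lost | 4 lost |
|---|---|---|---|---|
| 64 | 97.6% | 97.4% | 97.2% | 96.8% |
| 56 | 95.7% | 95.4% | 95.0% | 94.3% |

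**The case against.** A reader might infer that the plan deletes the primary value of every such subject. The documents do not say so. Section 6.7 depends on the drug having been received after the procedure, and 6.6 limits itself to the analysis of AEs and medication. A drug with a recorded stop of 4 September was not received after 20 September, and 6.6 leaves that stop unchanged. This objection stands: deletion is possible, not automatic. It does not clear the plan, because a programmer holding an imputed start on Day 0 and a recorded stop before it is given no rule for choosing.

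A reader might also infer that AE tables would be inflated. They would not. AEs are collected from consent, and SAP 9.7 reports incidence through Day 180 with no split at the procedure, so an event is counted once wherever its onset is placed. Only its listed dates and study day are wrong.

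Nor does the 51% mean that half of subjects are affected. It describes calendar opportunity. Sites must establish steroid timing to apply exclusion s, and SAP 5.2 has queries on the primary endpoint resolved, or judged unresolvable, before the analysis. Affected records may be few or none.

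Finally, no direction of bias is shown. A pair would be lost because of a drug record that precedes treatment.

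**Conclusion.** The fault in 6.6 is real and can be read directly from the text. A start or onset can be placed after its recorded end, and a prior record classed as during treatment. It affects drugs with the day missing and AEs with the day, or day and month, missing. The certain effects, where such records exist, are a wrong prior-versus-concomitant classification and wrong onset days in the AE listings.

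The effect on the primary endpoint is conditional. It needs the imputed start to be used for 6.7. Among classes with a stated washout, it also needs an oral, rinse or nebulized steroid that ended earlier in the procedure month, with a procedure on day 16 or later. The documents give no frequency. The power cost is small: 95.7% to 95.4% for one pair lost from 56, and 97.6% to 97.4% from 64, under the SAP's own effect size and SD. The reason to correct it is that a valid pair should not be dropped for a missing day, and that the plan should settle the choice before the data are seen.

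**What to change.** In SAP 6.6:

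- Shift a partial start or onset to the baseline date only if the stop or outcome date is missing, is partial but compatible with a date on or after baseline, or is recorded on or after baseline.
- Otherwise use the first of the month (1 January for AEs with only the year known) and class the record as prior. These are the fallbacks that 6.6 already has. They may fall before consent, and serve only to place the record before Day 0.
- State that an imputed start or onset may never follow a recorded stop or outcome date.

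In SAP 6.7, state that a steroid or biologic counts as post-procedure only if its recorded stop is not before Day 0.

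Do not add a rule that classes a course with both days missing as prior because washout was confirmed. For a procedure on days 1 to 15, a washout-compliant course of the 14-day class cannot have ended earlier in that month. For parenteral steroids this holds on every date. A course recorded in that month would then lie on or after the procedure, and such a rule would relabel true post-procedure use as prior. Query those records before the primary analysis.

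The cost is a few sentences in 6.6, one in 6.7 and one added condition in the date-derivation code. Sample size, endpoints, visits and clinical rules do not change.

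### SAP 6.6: the rule for medication starts with only the year known tests the missing month, so every such start defaults to 01 January

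*SAP*

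**What the plan says.** SAP 6.6 completes partial dates for a stated purpose: "a complete date will be established in order to identify AEs or medication as occurring during treatment or not". For medications, the case headed "Missing start day and month, but year present" has two branches. The first applies under the condition "If baseline visit occurred in the same month in the same year as the occurrence of the medication" and assigns the baseline visit date. The second reads "Otherwise, the start day and month is set to 01 January (e.g., XX-XXX-2021 is considered as 01-Jan-2021".

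The adverse-event rule in the same section, for an onset with day and month missing, has the condition "If baseline visit occurred in the same year as the occurrence of the AE" and then assigns the baseline date. It does not mention the month.

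For a medication stop with the same parts missing, 6.6 says "The stop day and month is set to 31 December". SAP 6.2.1 fixes the reference point: "Study day is calculated relative to the date of Day 0 (baseline").

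Three places use the timing of medication:
- SAP 6.7, on prohibited corticosteroids through Day 45 and on biologics: "Continuous efficacy endpoints will be set to missing for subjects who received any of the following not allowed medication post-baseline procedure". Binary endpoints become treatment failures.
- SAP 9.3.4, the sensitivity analysis for interventions, which acts when a subject initiates oral steroids before Day 45.
- Protocol 9.5, which reports the first use of each listed intervention through Day 180.

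**The concern.** The medication condition needs a piece of information that the case itself declares absent. The month is missing, so a match of months can never be shown, and the branch giving the baseline date is dead text. The wording fits the case just above it, where month and year are both known, and was probably carried down from there. Nothing in the SAP gives a reason for treating medications differently from adverse events here.

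The default also has a direction. 01 January precedes every other baseline date in that year, so a steroid begun after the procedure is dated before it. If that date decides whether the drug was a rescue, the subject is handled as unrescued. Left alone, the programmer must either code an unreachable branch or depart from the SAP without a record.

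**Working it through.** **Inputs.** The two rules, the stop-date rule and the Day 0 definition come from SAP 6.6 and 6.2.1. The sizing figures (80 randomized, 20% non-evaluable, mean difference 9 mm², SD 18 mm²) come from SAP 4.4. Let B be the baseline date and y the reported year.

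**Rules as written, with day and month missing**
- Medication: start = B if year and month both match B; otherwise 01 January of y. The month is unknown, so the result is always 01 January of y. This assumes that a condition which cannot be evaluated counts as not met; the SAP offers no third branch.
- Adverse event: onset = B if y = year of B; otherwise 01 January of y.

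**The SAP's own example.** XX-XXX-2021 becomes 01-Jan-2021. With a baseline of 01-Jun-2020, both rules reproduce it, because the years differ.

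**One record.** Baseline is 15-Sep-2021 and the true rescue start is 05-Oct-2021 (Day 20), recorded as XX-XXX-2021.

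| Quantity | Date | Days from baseline |
|---|---|---|
| Start, medication rule as written | 01-Jan-2021 | -257 |
| Start, adverse-event wording | 15-Sep-2021 | 0 |
| Stop, if also year-only | 31-Dec-2021 | 107 |

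**All 2021 baselines, true starts on Days 1 to 44**
- Combinations: 365 × 44 = 16,060.
- Start falls in the next year: 1 + 2 + … + 44 = 990. Their 01 January start lies after baseline, so they are unaffected.
- Start falls in the baseline year: 16,060 − 990 = 15,070.
- Exception, baseline on 01 January itself: 44.
- Dated before Day 0 as written: 15,070 − 44 = 15,026, or 99.7% of 15,070. With the adverse-event wording: 0.
- Year-only stop dates before Day 0: 0 of 15,070.

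These counts describe the rule. They do not estimate how many trial records are affected.

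**The opposite case.** Take a medication started and stopped in March, before a September procedure, with a year-only start and a recorded stop. Here 01 January is on the correct side of Day 0. The adverse-event wording, copied unguarded, would give a September start after a March stop.

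**What each use of timing turns on**

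| Place | Event | Effect of a false 01 January start |
|---|---|---|
| SAP 6.7 | Drug *received* post-baseline | None if judged by start-to-stop overlap; missed if judged by start date |
| SAP 9.3.4 | Oral steroids *initiated* before Day 45 | Start appears to precede the procedure; rescue can be missed |
| Protocol 9.5 | First use through Day 180 | Dated before Day 0 if start date is used |

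**Size of one missed record in 9.3.4.** Evaluable pairs: 80 × 0.80 = 64. Standard error: 18/√64 = 2.25 mm². For a rescue on the treatment side or both sides, the plan sets the side-to-side difference to zero. If it is missed, the observed difference d stays and the mean moves by d/64:
- d = 9: 9/64 = 0.14 mm², or 0.06 standard errors.
- d = 9 + 2 × 18 = 45: 45/64 = 0.70 mm², or 0.31 standard errors.

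For a rescue on the control side only, the plan sets the control area to zero. Missing it lowers the estimated difference by the control area divided by 64. The documents give no expected control area.

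**The case against.** The strongest reply is that the SAP nowhere says the start date alone separates prior from post-procedure medication. Section 6.6 asks whether a drug was occurring during treatment, and it completes stop dates for that same purpose. Section 6.7 acts on drugs received, not drugs started. A true rescue has a stop date after Day 0, recorded or imputed, so an interval from 01 January to that stop spans the procedure and 6.7 still applies. This stands. It removes the inference a reader might draw, that a rescued subject necessarily passes into the primary t-test as an unaffected case.

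A reader might also infer that every year-only start in the procedure year is misplaced. That is not so: a medication that truly began earlier that year is left on the correct side of Day 0.

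Other safeguards also count. Concomitant medication is collected at every visit, interventions go on the follow-up forms as well (protocol 15.2), source data are verified (protocol 19.6), and queries on primary and key secondary endpoints are closed before the Day 45 analysis (SAP 5.2). A year-only date for a steroid begun between closely spaced visits should be uncommon. The 9.3.4 rules also need side and cause, which a medication date does not supply.

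These points do not make the rule correct. No overlap definition is written down, 9.3.4 is worded by initiation, and the SAP does not say that another form overrides an imputed date.

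**Conclusion.** The defect holds as a drafting error in the current SAP text, with high confidence: one branch is unreachable, and true post-procedure starts in the procedure year are dated before Day 0 unless baseline is 01 January.

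The consequence is limited. The clearest exposure is the 9.3.4 sensitivity analysis, together with any output that classifies by start date. Whether the primary analysis under 6.7 is touched depends on an unstated choice between start date and overlap; under overlap it is not. On the SAP's planning figures, one missed record on the treatment side or both sides moves the sensitivity estimate by about 0.14 mm² at the expected difference, and by 0.70 mm² for a difference two SDs above it. One record is therefore unlikely to change the conclusion. The number of affected records is not given and is probably small.

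The point is worth correcting because the rule gives a wrong date and the correction is cheap, not because the primary result is shown to be at risk.

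**What to change.** In SAP 6.6, for medication starts with day and month missing:
1. Delete *in the same month*, so that a start in the baseline year is assigned to the baseline date.
2. Add an exception: if the recorded or imputed stop date is before baseline, keep 01 January. Complete the stop date first.
3. State that a medication counts as post-baseline if its start-to-stop interval includes any time after the procedure. Say also that an imputed Day 0 start counts as initiated after the procedure for 9.3.4.

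The cost is a few lines in the SAP and a small change to the derivation program. It should be made before the blind is broken for the Day 45 analysis.

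The downside is that some same-year medications that began before the procedure and continued past it will be given a Day 0 start. That is conservative in the sense of erring towards counting post-procedure use. It does not always work against the implant, since 9.3.4 sets the control area to zero for a control-side rescue. The exception also cannot help when the stop is year-only, because 31 December of the baseline year is never before baseline. Such records should be queried.
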